# 7.2.10 Anti-Drug Antibody (ADA) to AVID100 (Central Lab)

(To assess the potential immunogenicity of AVID100; serum to be isolated; residual sample material may be used for biomarker assessments (**Section 7.6.2**))

- Cycle 1
  - Day 1 (prior to SOI)
- Each cycle thereafter
  - o Day 1 (prior to dosing)
- EOT
- 1M FUP
- As clinically indicated in the event of an IRR

Note: Whole blood (~ 5 mL) to be collected in serum acquisition tubes at each of the indicated timepoints (see also **Appendix A**; Schedules of Events). In the event that a collected serum sample is inadequate or insufficient for ADA analysis, the analysis of ADA can be done using a PK serum sample from the same time point, if available.

Detailed procedures for collection, handling, and shipment of samples will be provided by the Sponsor (or designee) in the study Laboratory Manual (or other similar document).

# 7.2.11 Pregnancy Testing

(beta-human chorionic gonadotropin [ $\beta$ -hCG] in WOCBP; serum at screening, urine or serum thereafter; negative test must be confirmed within  $\underline{2}$  working days prior to first dose of study drug)

- Screening
- Cycle 1
  - o Day 1 (within  $\leq$  2 working days of dosing)
- EOT
- As clinically indicated

\*Need not be performed prior to the first dose of Cycle 1 if  $\leq 7$  days since screening

### 7.2.12 Electrocardiogram

(To include standard 12-lead ECG with measurement of PR interval, QRS duration, QT interval, and QTc interval [msec], as well as heart rate [BPM])

(To be evaluated locally; to be performed after patient has been supine for  $\geq$  10 minutes) (Repeat subsequent time points in triplicate separated by 5 minutes for 4 cycles in patients with a QTc that is either: a) > 500 msec; b) increased by 60 msec over baseline\*; or c) decreased by 20 msec under baseline\*)

- Screening
- Cycle 1
  - o Day 1
    - Prior to SOI
    - EOI (± 5 min)
    - 30 minutes after EOI (± 5 min)
- Subsequent 4 cycles, if QTc abnormalities are observed during Cycle 1
  - o Day 1
    - Prior to SOI (in triplicate)
    - EOI (± 5 min) (in triplicate)
- EOT
- As clinically indicated\*\*

# 7.3. Safety Assessments (2)

(To be performed within 28 days [+2 days] prior to first dose of study drug, provided no antineoplastic therapy has been delivered between safety assessment and first dose of study drug)

## 7.3.1 Ophthalmology Examination

(To include slit lamp evaluation, tests to evaluate corneal integrity and visual acuity assessment)

- Screening
- End of Cycle 2\*,\*\*
- EOT\*\*
- As clinically indicated

\*When evaluating QTc, baseline should be considered the ECG immediate preceding the start of study drug infusion on the day of assessment.

\*\*In the event of significant electrolyte abnormalities, the evaluation frequency should be increased to include additional evaluations between the scheduled assessments, as clinically indicated

\*End of Cycle assessments may be conducted at any time during the week prior to Day 1 of the next cycle.

\*\*May be combined if patient discontinues treatment at End of Cycle 2

Note: See Appendix H (Recommendations for Management of Keratitis and Rash) for dose modification instructions for keratitis (corneal inflammation/ulceration)

#### 7.3.2 MUGA Scan or Echocardiogram

(For measurement of LVEF; to be performed ONLY in patients with a history of CHF; individual patients should be followed with the same testing procedure throughout the study)

- Screening
- EOT
- As clinically indicated

Note: Assessment of LVEF will not be performed routinely in all patients. Patients with a history of CHF will have either a MUGA scan or echocardiogram at Screening.

# 7.3.3 Pulmonary Function Testing

(PTF to include spirometry and diffusing capacity [DLco] to assess for evidence of pulmonary fibrosis. Spirometry assessments are to include but are not limited to: forced vital capacity [FVC], forced expiratory volume in 1 second [FEV1], forced expiratory flow 25% to 75% [FEF25-75], functional residual capacity [FRC], residual volume [RV], and total lung capacity [TLC].)

- Screening
- EOT
- As clinically indicated

# 7.3.4 Chest Radiography

(To include posterior to anterior[PA] and lateral views of the chest to assess for evidence of pulmonary fibrosis)

- Screening
- EOT
- As clinically indicated

Note: Diagnostic imaging (CT/MRI) being conducted to for Assessment of Disease will be utilized to assess for evidence of pulmonary fibrosis while patients are on (see **Section 7.4.3**; Diagnostic Imaging for Assessment of Disease (and Pulmonary Status).

### 7.4. **Disease Assessments**

(Screening assessments to be performed within 28 days (+ 2 days) prior to first study drug dose)

#### 7.4.1 EGFR Tumor Status Determination

(To include assessment of FFPE tumor tissue; by local or central evaluation of archival tissue or verification by previous pathology report during Phase 1a and by central evaluation of tumor tissue [archival or from a recent biopsy] during Phase 2a)

Phase 1a Dose-Escalation Cohorts: Optional (Local or Central Lab)

Phase 2a Expansion Cohorts: Required (**Central Lab**); tumor must be EGFR-positive by IHC as specified\* for patient to be eligible for enrollment. If archival tissue is not available patient must be willing to undergo pre-dosing biopsy from a primary or metastatic tumor site\*\*

- Screening\*\*\*
- Post-dosing: Upon request of the Sponsor based on other study findings, after discussion with the Investigator; if available a request may be made for collection of additional archival tissue for exploratory biomarker assessments (Section 7.6.1): Optional
- \* DAKO EGFRpharmDX™IHC kit system technology to be utilized. For this study, EGFR-positive staining is defined as  $\geq 3+$  intensity in  $\geq 50\%$  of tumor cells or  $\geq 2+$  intensity in  $\geq 75\%$  of tumor cells for mTNBC; or 3+ intensity in  $\geq 50\%$  of tumor cells for SSCHN and Sq-NSCLC, whether it is complete or incomplete circumferential staining.
- \*\*Sufficient FFPE tissue must also be available for submission to a central analytical laboratory for other study-related evaluations (see **Section7.6.1**; Exploratory EGFR Studies in Tumor Tissue).
- \*\*\*The trial will prescreen patients for EGFR Tumor Status Determination before entering patients into screening for the treatment portion of the trial. The site should use a separate prescreening informed consent form. Prescreening may be performed outside the 28 (+ 2) day screening period to allow adequate turnaround time for receipt of results, provided separate informed consent has been obtained.

# 7.4.2 Tumor Marker Measurement (Phase 1a only)

(As indicated by tumor type)

- Screening
- End of Cycle 2 (and every even-numbered cycle thereafter)\*
- At least 4 weeks following documentation of an OR
- EOT (if > 6 weeks since previous assessment)
- 1M FUP (if PD was not documented before or at EOT)
- Extended Follow-up\*\* (in the event of an ongoing OR or SD at EOT)
  - o Every 3 months during the first year of follow-up
  - o Every 6 months thereafter

\*End of Cycle assessments may be conducted at any time during the week prior to Day 1 of the next cycle.

\*\*To continue at the intervals specified until disease progression or another therapeutic intervention is initiated; documentation may be submitted in writing, an in-person visit will not be required.

# 7.4.3 Diagnostic Imaging for Assessment of Disease (and Pulmonary Status)

(To include diagnostic imaging by computerized tomography [CT] or magnetic resonance imaging [MRI] of the chest with each evaluation (for disease evaluation where indicated, and to assess for evidence of pulmonary fibrosis) plus abdomen and pelvis, and other sites as indicated based on tumor type and clinical judgment in order to assess the status of the underlying malignancy. Use of contrast is preferred but is at the discretion of the Investigator, as medically indicated.

The same method(s) of disease evaluation and the same technique should be used throughout the study. The location and dimensions of "marker" lesions, where such information is available, will be documented on the patient's eCRF. Standard response criteria will be applied for disease assessments and response evaluations [see **Appendix F**; Measurement of Effect]).

- Screening
- End of Cycle 2 (and every even-numbered cycle thereafter)\*
- At least 4 weeks following documentation of an OR
- EOT (if > 6 weeks since previous assessment)
- 1M FUP (if PD was not documented before or at EOT)
- Extended Follow-up\*\* (in the event of an ongoing OR or SD at EOT)
  - o Every 3 months during the first year of follow-up
  - o Every 6 months thereafter

If PD is documented at any time no further disease assessments will be required. Patients with documented PD will be discontinued from further treatment with study drug so that alternative management of their malignancy may be considered.

To be assigned a status of partial response (PR) or complete response (CR), changes in disease status must be confirmed by repeat studies performed 4 weeks (+ 7 days) after the criteria for response are first met. In the case of SD, follow-up measurements must have met the SD criteria at least once after study entry at for a minimum duration in general not less than 8 weeks.

\*End of Cycle assessments may be conducted at any time during the week prior to Day 1 of the next cycle.

\*\*To continue at the intervals specified until disease progression or another therapeutic intervention is initiated; documentation may be submitted in writing, an in-person visit will not be required.

In the event of an ongoing OR or SD at the EOT, data will continue to be collected on the duration of OR or SD, as well as on the overall time to PD.

Imaging data (imaging studies and derived assessments) will be stored according to usual practice by the sites and will be available upon request for potential review by the Sponsor or an independent radiology reviewer.

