Because of the risk of pulmonary toxicity that has been observed with ADCs and agents inhibiting EGFR, and because a single patient on the Phase 1a segment of this trial receiving a dose of 270 mg/m² developed pneumonitis considered related to AVID100, patients with a history of or evidence of interstitial fibrosis will continue to be excluded from entry into the trial. Patients will be assessed using chest CT every 6 weeks (when disease assessments are scheduled) regardless of whether these imaging studies are required for tumor assessment. Patients will also be evaluated by regular evaluation of oxygen saturation using pulse oximetry, physical exams and queries regarding all adverse events with a detailed assessment of potential

pulmonary adverse events. Pulse oximetry will be conducted prior to and following all infusions of AVID100 throughout the study, and decreases in oxygen saturation will require further evaluation. In the event of patient-reported symptoms of pulmonary toxicity or Investigator-assessed symptoms or signs of potential pulmonary adverse effects, additional studies including interval chest imaging studies will be performed. If pulmonary findings on imaging studies (e.g., evidence of pulmonary fibrosis, interstitial pneumonitis, acute respiratory distress syndrome) or clinical evidence of pulmonary adverse effects are detected, administration of AVID100 will be permanently discontinued and pulmonary consultation will be obtained to consider additional appropriate diagnostic procedures and/or therapeutic interventions.

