#### **6.5.3.6.** Schedule

Study drug is to be administered once every 3 weeks (Q3W) on Day 1 of each cycle (3 weeks [21 days] equals 1 dosing cycle).

End of Cycle 1 (EOC1) assessments are to be performed no sooner than C1/D21 (-2 days). Subsequent cycles may be administered Q3W ( $\pm$  2 days), unless further delay is required to allow for amelioration of toxicities.

# 6.6. Cycle 1

A minimum of 1 cycle of AVID100 will be administered, if tolerated. Any interruptions in dosing and the reasons for such interruptions must be documented. If an AE is the cause for dosing interruption, it must be detailed on the Adverse Events page of the eCRF. Determinations regarding cohort escalation, DLTs, and MTD will be based on the toxicities observed during this 3 week period (Cycle 1) of treatment.

- Patients completing Cycle 1, in the absence of a DLT, will be considered to have tolerated the AVID100 regimen.
- Patients must receive their full planned dose of AVID100 during Cycle 1 in order to be considered evaluable for tolerability unless dose reduction, interruption, or discontinuation was the result of a DLT.
- Dose-Escalation Cohorts: Patients will be replaced, if necessary (e.g., received < 1 full dose of AVID100 plus follow-up through EOC1 [C1/D21 {-2 days]}]) for any reason other than a DLT), to allow for a thorough assessment of the tolerability in any dose cohort.

- All enrolled patients will be considered in the assessment of safety and tolerability.

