### 6.6.3.3. Rules for Tolerability in Phase 2a

The criteria for tolerability during Phase 1a will apply to Phase 2a Expansion Cohorts. Safety will be reviewed on an ongoing basis to determine if the dose and schedule chosen based on the Phase 1a dose escalation is safe and well-tolerated in expanded populations of patients with the tumor types selected for the expansion cohorts (mTNBC, SCCHN, and Sq-NSCLC). Should it be determined that the dose is not well-tolerated (i.e.,  $\geq 33.3\%$  of patients in an expansion cohort experience a Cycle 1 DLT), the safety of that dose level will be re-evaluated and the next lower dose with established tolerability in Phase 1a will be administered to subsequent patients.

An exception will be the occurrence of toxicity suggesting organ damage (e.g., pulmonary fibrosis, drug-induced liver injury) occurring in  $\geq 2$  patients within an expanded cohort, in which case further accrual to that cohort will be discontinued.

# 6.7. Continued Therapy After Cycle 1

Upon completion of Cycle 1, in the absence of unacceptable toxicity or disease progression, patients may continue receive additional cycles of study drug Q3W ( $\pm$  2 days), unless further delay is required to allow for amelioration of toxicities. Administration of subsequent dosing cycles is allowable at the discretion of the Investigator, provided the patient meets the retreatment criteria listed below. Additional cycles should be initiated as soon as possible, but not longer than 2 weeks after the completion of the previous cycle, if feasible.

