#### **6.7.1** Retreatment Guidelines

Clinical judgment will be used when determining whether it is advisable to continue a patient on to the next cycle(s) of dosing. In order to start any new cycle a patient must meet the following criteria:

- ANC  $\geq$  1,000 per mm^3
- Platelets  $\geq 75,000 \text{ per mm}^3$
- Any ongoing AEs should NOT meet the criteria for DLT.
- Any ongoing AEs should have either ameliorated to ≤ Grade 1 severity, returned to baseline status, or resolved, with the exceptions of Grade 2 alopecia, clinical events that are being adequately controlled with best supportive care (e.g., nausea, vomiting, diarrhea, fatigue), and asymptomatic laboratory abnormalities that are considered clinically insignificant or that are resolving with medical therapy.

Should any one of the criteria above not be met, dosing of study drug must be delayed.

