Patients requiring a more extensive or major surgical procedure (e.g., resection of hepatic metastases) should have protocol therapy interrupted, but may resume treatment once fully recovered and at a minimum 2 weeks after the procedure. Protocol retreatment criteria must be met.

• Allowed Dosing Delays: Following Cycle 1 and completion of the DLT assessment period, and only if indicated, dosing may be briefly interrupted for situations other than treatment-related AEs such as medical (or surgical events) or logistical reasons not related to study therapy. Participants should be placed back on study therapy within 2 to 3 weeks of the scheduled interruption, unless otherwise discussed with the Sponsor.

Information on all concomitant therapies administered, as well as other interventions or procedures occurring during the trial period, must be recorded on the appropriate page of the patient's eCRF.

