### 7. STUDY ASSESSMENTS

All patients will be assessed by scheduled clinical, laboratory, and other diagnostic assessments throughout the study.

All efforts should be made to perform assessments as close as possible to the scheduled time points. The projection of visit days within each cycle should be made from Day 1 of the respective cycle. Visit windows are provided below. Study assessments are to be performed as follows:

- Screening evaluations are to be performed within 14 days prior to first study drug dose, unless otherwise specified (for exceptions see Section **7.2.11**; Pregnancy Testing, **Section 7.4**; Disease Assessments).
- The day of first administration of study drug will be considered Day 1 of study.
- Cycle 1/Day 4 evaluations may be conducted  $\pm 1$  day
- Dosing and on-study evaluations (including laboratory assessments) are to be performed on or about the indicated study day (i.e., ± 2 working days) (a slightly longer allowance for routine assessments is permissible in the event of scheduling difficulties associated with weekends, holidays, etc.).
- End of Cycle assessments may be conducted at any time during the week prior to Day 1 of the next cycle, including on Day 1 of the next cycle, prior to dosing.
- End of Treatment (EOT)\* evaluations are to be performed within approximately 10 days following the decision to discontinue treatment, or before initiation of a new treatment, whichever occurs first.
- 1 Month Follow-up (1M FUP)\* evaluations are to be performed approximately 30 days (+7 days) following the last dose of study drug (i.e., as all patients are to be followed for a minimum of 30 days after study drug discontinuation in order to monitor for the occurrence of AEs).

\*Given the Q3W dosing frequency, EOT and 1M FUP evaluations may be combined in those situations where scheduling coincides, provided a minimum of 30 days of post-dosing follow-up have been observed.

Note: When a patient discontinues treatment with study drug, for any reason, every effort will be made to collect routine EOT evaluations as well as subsequent 1M FUP evaluations, per protocol, until all protocol-specified assessments have been conducted.

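### Imaging follows cycle number, so dosing delays of more than a week can break the 6-week scan interval in Section 2.4.2, and Appendix F gives 8 weeks

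*Combined protocol and SAP*

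**What the plan says.** - **Anchor.** Section 7.4.3 places on-treatment imaging at "End of Cycle 2 (and every even-numbered cycle thereafter". Section 7.4.4 and Table 7 use the same anchor for response assessment.
- **Window.** The footnote to 7.4.3 states: "End of Cycle assessments may be conducted at any time during the week prior to Day 1 of the next cycle". Section 7 adds: "The projection of visit days within each cycle should be made from Day 1 of the respective cycle". The scan window therefore moves with the next dose.
- **Cycle length.** Section 6.5.3.6: "3 weeks [21 days] equals 1 dosing cycle".
- **Delays.** If retreatment criteria fail, Section 6.7.1 says: "Should any one of the criteria above not be met, dosing of study drug must be delayed". Section 6.7 gives the 3-weekly schedule "unless further delay is required to allow for amelioration of toxicities", and asks for the next cycle within 2 weeks of completing the previous one where feasible. For non-toxicity interruptions, Section 6.12 says: "Participants should be placed back on study therapy within 2 to 3 weeks of the scheduled interruption". No section tells sites to scan on the calendar while a dose is held.
- **Other statements of the interval.** Section 2.4.2, on pulmonary risk: "Patients will be assessed using chest CT every 6 weeks (when disease assessments are scheduled". The introduction to Appendix F (Table 14) sets response re-evaluation at 8-week intervals.
- **Endpoints.** Section 14.3.3.1 ends TTP on the date progression is first recorded, or on death, and counts disease stabilisation of at least 8 weeks in the DCR. Sections 14.2 and Appendix I bring durability and stabilisation beyond 8 weeks into the cohort-expansion decision.

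**The concern.** When progression is found by imaging, its recorded date depends on when the scan is done. If the scan waits for the next dose, a treatment-related event (the hold) also sets the assessment time. TTP, SD duration and DCR then partly reflect tolerability as well as tumour behaviour, and in a single-arm trial no control group would reveal it.

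The same scans carry a safety role. Pulmonary function tests and chest X-ray are scheduled only at Screening and end of treatment (7.3.3, 7.3.4), and 7.3.4 relies on the disease scans while patients are on treatment. A patient held for toxicity may have this imaging later than Section 2.4.2 implies.

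The passages also conflict with no delay at all: Section 2.4.2 and Appendix F give different intervals, and Section 2.4.2 specifies chest CT where 7.4.3 allows CT or MRI.

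**Working it through.** **1. The plan's own figure.** Two cycles × 21 days = 42 days = 6.0 weeks. Cycle 3 Day 1 is Day 43, and the scan window is Days 36–43. The 6 weeks in Section 2.4.2 is reproduced when nothing is delayed.

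**2. Effect of delay.** Let D be the total dosing delay, in days, before the scan. The window runs from 35 + D to 42 + D days after Cycle 1 Day 1. It still contains day 42 when 35 + D ≤ 42, that is, D ≤ 7.
- D = 14 (one 2-week delay): days 49–56, weeks 7–8.
- D = 21 (one 3-week interruption): days 56–63, weeks 8–9.
- D = 28 (2-week delays before both Cycles 2 and 3): days 63–70, weeks 9–10.

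**3. Mean recorded TTP.** The documents give neither the true TTP distribution nor the delay frequency. Assume exponential TTP with median m weeks, so P(T > t) = 2^(−t/m), m from 6 to 24, every progression found at a scheduled scan, and scans at the end of the window. With scans every Δ weeks, mean recorded TTP = Δ / (1 − 2^(−Δ/m)).
- m = 6: Δ = 6 gives 6/0.5 = 12.00; Δ = 8 gives 8/0.6031 = 13.26 (+1.3); Δ = 10 gives 10/0.6850 = 14.60 (+2.6).
- m = 24: Δ = 6 gives 6/0.1591 = 37.71; Δ = 8 gives 8/0.2063 = 38.78 (+1.1); Δ = 10 gives 10/0.2508 = 39.87 (+2.2).

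Here Δ = 8 means a 2-week delay in every pair of cycles, and Δ = 10 a 2-week delay in every cycle.

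For a single 2-week delay before the first scan, scans fall at weeks 8, 14, 20… instead of 6, 12, 18…. A patient whose true progression lies in weeks 6–8, 12–14 and so on is recorded 4 weeks earlier; everyone else is recorded 2 weeks later. The share recorded earlier is p = (1 − 2^(−2/m)) × 2^(−6/m) / (1 − 2^(−6/m)), and the mean shift is 2(1 − p) − 4p = 2 − 6p.
- m = 6: p = 0.206, shift +0.76 weeks.
- m = 24: p = 0.297, shift +0.22 weeks.

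So 70–79% of patients are recorded later and 21–30% earlier. Simulation gave the same results.

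**4. The median.** Section 14.3.3.1 reports a Kaplan-Meier median. If all patients share one scan grid, the recorded median is the first scan at or after the true median. A true median of 9 weeks is recorded as 12 on the 6-week calendar and 14 after one delay; a true median of 7 weeks is recorded as 12 and 8. The median can therefore move either way.

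**5. The 8-week SD threshold.** Eight weeks is 56 days. An on-schedule first scan (days 35–42) cannot show SD at 8 weeks. With D = 14 the last day of the window reaches day 56, and with D = 28 the whole window lies beyond it. Under 7.4.3, which asks for SD criteria to be met at not less than 8 weeks in general, the postponed first scan can qualify alone; an on-schedule patient needs the second scan, in weeks 11–12.

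**The case against.** - **The 6-week CT is delivered when dosing is on time.** This stands. Section 2.4.2 ties the interval to scheduled disease assessments, so it describes the nominal plan. A reader might infer that the promised CT is not delivered; the documents support only that it is not guaranteed under delay.
- **Not every delay moves the scan.** This stands. The window absorbs up to 7 days. A hold before Cycle 3 may also be decided on pre-dose laboratory results after the scan has been done, and nothing requires a repeat.
- **Long repeated delays should be uncommon.** Partly stands. Under Section 8.3.2.1 a related Grade 3 or 4 toxicity that delays dosing beyond 2 weeks is a DLT, leading to dose reduction or discontinuation. A reader might take 70/42 = 1.67 as a 67% inflation of TTP; that is one near-worst-case patient who progressed before week 6 with nothing found until week 10.
- **Bias in proportion to delay.** A reader might infer this for every patient. Working steps 3 and 4 show that it fails: some patients are recorded earlier, and the median can fall. Deaths count on their own date, and progression may be documented at any time.
- **Six weeks of average participation.** The note to Table 9 might suggest that the first scan usually sets the TTP date. It is a planning figure for blood volumes, not an assumption about TTP.
- **Pulmonary safeguards remain.** This stands in part. Section 2.4.2 provides oximetry around infusions and interval imaging for symptoms or signs. Pulmonary function tests and chest X-ray are done at end of treatment, with CT or MRI if more than 6 weeks have passed. What remains uncovered is the asymptomatic patient on hold.
- **No inference is planned.** This stands. Section 14.1 excludes inferential tests, and the numerical expansion rules in 14.2 use response counts; durability and SD are additional considerations.

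**Conclusion.** The point holds as a scheduling weakness and an internal inconsistency. Cumulative delays of more than 7 days before a scan can stretch the interval from 6 weeks to about 8 (one 2-week delay) or about 10 (2-week delays before both Cycles 2 and 3). The chest CT interval in Section 2.4.2 is then not guaranteed. Appendix F conflicts with it regardless of delay.

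Mean recorded TTP rises by 0.2–0.8 weeks for one 2-week delay and by 2.2–2.6 weeks if every cycle is delayed. These figures rest on exponential TTP with a median of 6–24 weeks and detection only at scheduled scans; the overall effect depends on a delay frequency that the documents do not give. A delayed first scan can also make SD easier to qualify for, and SD beyond 8 weeks feeds the expansion decision. The consequence is for descriptive single-arm endpoints and that decision. A reader might infer a biased treatment comparison; the trial has no comparator, so none exists.

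**What to change.** Reconcile Sections 2.4.2, 7.4.3 and 7.4.4, Table 7 and Appendix F to one interval. Count it in calendar weeks from Cycle 1 Day 1, with a stated window, independent of dosing delays, until progression or new anticancer therapy. Reconcile chest CT (2.4.2) with CT or MRI (7.4.3). Which interval and modality to adopt is for the sponsor to decide; the statistical need is that timing does not depend on dosing.

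The cost is wording in those places. Some scans will not coincide with a cycle visit, and patients with delays may have an occasional extra scan relative to doses received.
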